5.8.1 Additional safety tables

A table of ISR grade by vaccination number will be produced.

CRUKD/17/003 RAP Version: 2.0 09Mar2023 FINAL

Table 12: Summary of Injection Site Reactions by Grade and Vaccination Number (*Safety Population*)

ISR Grade	Vaccination number at onset						
	Total	1	2	3	4	5	6
1	N	N	N	N	N	N	N
2							
3							
4							
5							

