5.10 General data conventions

There is only one dose level for this study, as specified in the study protocol. Patients who deviate from the assigned dose and/or schedule will be clearly described in the CSR with regards to their treatment modification and if applicable in the list of protocol deviations (Section 5.4).

Continuous variables will be summarised and presented with summary statistics.

The median OS will be presented.

Categorical variables will be summarised in frequency tables. Percentages in the summary tables will be rounded and may therefore not always add up to exactly 100%.

The convention in Rave is that an unknown day resolves to 1st of the month and an unknown month resolves to January. Dates may be ordered by this; however, CRUK do not perform calculations on unknown dates except as stated below.

Durations of AEs: the start date of an AE is considered as Day 1 of the event and should be included in all duration calculations (i.e. if an AE starts and stops on same day, the duration should be reported as one day).

- For unrelated AEs, those with missing or partially completed end dates will not be excluded from analysis and the duration of the AE will be calculated from the first day of the month (if unknown) or first day of the year (based on RAVE conventions).
- For related AEs, prior to final data lock, an end date will be either i) confirmed AE end date or ii) stabilisation of AE. Cases where this is not possible are if the patient was lost to follow up. If lost to follow-up then the AE would stay as not recovered/not resolved. In this case duration would not be calculated.

Time to onset of AEs from IMP administration: the time to onset should be calculated from the date of the first AST-VAC2 vaccination and AEs occurring within a specific vaccination window (e.g. start date from date of 2nd vaccination to before date of 3rd vaccination) should also have times to onset calculated from the date of the last vaccination administered in that window (e.g. Vaccination 2). Onset time will be

calculated as 0 if the AE occurs on the same day as the dose; however, if the start time is missing, onset time will not be calculated (only applicable when the drug admin has a start time entered).

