AE assignment: AE is assigned to the vaccination number it begins in. This is regardless of whether the AE start time shows the AE started before the dose that day. The only exception is for the first vaccination; if 'Did AE occur prior to first dose' is checked then no vaccination number will be assigned.

Duration of treatment: this is from the day of the first vaccination until the day of the final vaccination. Duration of treatment will be described using summary statistics.

Completed vaccination: AST-VAC2 vaccinations are to be given once a week for 6 weeks. A patient is considered to have completed vaccination when vaccination data entered is for each of those expected weekly visits (despite dose modifications).

Treated patients: If the drug administration form in the eCRF has the 'date of vaccination' completed, this constitutes a treated patient.

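### At vaccinations 2 to 6, an adverse event recorded as starting before that day's dose is still assigned to that dose, so Table 12 can show an injection site reaction under a vaccination not yet given

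*SAP*

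**What the plan says.** SAP 5.10 (General data conventions) sets out the assignment rule: "AE is assigned to the vaccination number it begins in". The next sentence deals with an event on a dosing day whose start time is known: "This is regardless of whether the AE start time shows the AE started before the dose that day". The rule is relaxed once: "The only exception is for the first vaccination; if 'Did AE occur prior to first dose' is checked then no vaccination number will be assigned".

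The time-to-onset convention in the same section also works by date. Its example of a vaccination window is "start date from date of 2nd vaccination to before date of 3rd vaccination", and onset is "calculated as 0 if the AE occurs on the same day as the dose". It then adds a condition on times: "if the start time is missing, onset time will not be calculated (only applicable when the drug admin has a start time entered".

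The assignment is used in SAP 5.8.1: "A table of ISR grade by vaccination number will be produced". This is Table 12, whose columns are headed "Vaccination number at onset" and run from 1 to 6 after a total. Nothing in the SAP exempts ISRs, or vaccinations 2 to 6, from the rule.

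**The concern.** The rule is not a fallback for missing data. It applies when the recorded time shows that the dose had not yet been given. An ISR that began on the morning of vaccination 3, before the injection, can only be due to vaccination 1 or 2. The SAP still counts it under vaccination 3 and gives it an onset of 0 days.

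The error runs in one direction: an affected event can only move to a later dose and a shorter onset. In a table meant to show how ISRs develop over repeated vaccination, that can look like faster or increasing reactions. The pattern matters in this trial. Protocol 3.3.1 names injection site inflammation as the main potential toxicity, safety is the primary objective, and Protocol 9.2.4 lists timing relative to administration among the considerations for causality. Table 12 is the only summary table listed in SAP 6.2 that shows ISRs by vaccination number.

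The SAP's own logic also points the other way. It accepts that an event before dose 1 does not belong to dose 1, then drops that reasoning for doses 2 to 6. The first-dose exception does not help here, because no ISR to AST-VAC2 can precede dose 1.

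**Working it through.** The documents state no figure on this point, so there is none to reproduce. The check applies the SAP rule to a worked schedule and compares it with a rule that uses the recorded time.

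**Inputs from the documents**
- Six weekly vaccinations, 7 days apart, plus or minus 1 day (Protocol 1.5 and 5.2).
- Up to eight patients (Protocol 1.6).
- Date-based assignment, with same-day onset set to 0 (SAP 5.10).

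**Assumptions, for illustration only**
- Every dose is given at 12:00 on days 0, 7, 14, 21, 28 and 35.
- An ISR starts at 08:00 on the day of dose k, for k = 2 to 6.

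**Rules compared**
- SAP: assign to the latest dose whose date is on or before the event date. The result is dose k, and onset = 7(k − 1) − 7(k − 1) = 0 days.
- Time-based: assign to the latest dose actually given before the event started. The result is dose k − 1, and onset = 7(k − 1) − 7(k − 2) = 7 days.

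| ISR begins before dose | SAP column | SAP onset (days) | Time-based column | Time-based onset (days) |
|---|---|---|---|---|
| 2 | 2 | 0 | 1 | 7 |
| 3 | 3 | 0 | 2 | 7 |
| 4 | 4 | 0 | 3 | 7 |
| 5 | 5 | 0 | 4 | 7 |
| 6 | 6 | 0 | 5 | 7 |

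With the plus or minus 1 day window, the time-based onset is 6 to 8 days. It would be longer after a delayed dose.

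**Reach of the rule**
- Dosing days on which it can apply: at most 8 × 5 = 40, out of 8 × 6 = 48 patient-dosing days if all eight patients receive all six vaccinations.
- The dosing day is one calendar day in each interval of 6 to 8 days: 1/8 = 12.5% to 1/6 = 16.7% of days. Only the hours before the injection matter. This is a share of days, not of events.
- The documents give no ISR rate and no frequency of same-day pre-dose onset, so the expected number of misplaced events cannot be computed.

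**What moves and what does not.** Reading the N in Table 12 as a count of events, one count moves from column k − 1 to column k within the same grade row. The row total stays the same. Onset from the first vaccination, which SAP 5.10 also calls for, is unaffected.

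**The case against.** The strongest defence is that this is a transparent, prespecified convention based on dates, that it touches only a narrow edge case, and that no key result depends on it. Most of this stands.

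- Overall AE counts, grades, investigator-assessed causality, treatment-emergent status, the stopping criteria and the number of participants with ISRs by grade do not use the vaccination number. No formal analysis is planned.
- A reader might infer that late reactions in general are pushed forward by one dose. They are not. An ISR whose start date falls before the next dosing date stays with the right vaccination.
- A reader might take the AE assessment before each dose (Protocol 7.2) as evidence that such events are common. That assessment covers everything since the previous visit, and an ISR found that morning but begun earlier keeps its earlier date. It shows only that pre-dose onsets on a dosing day can be captured.
- A reader might express the shift as one patient in eight, or 12.5 percentage points per cell. The Table 12 template shows N only, with no percentage and no column denominator, so that figure has no basis.
- SAP 6.2 lists no time-to-onset table, so the onset of 0 reaches no planned summary table.
- Patient-level listings of adverse events and of vaccine administration are planned (SAP 6.1). Table 12 is the only by-dose summary of ISRs, but not the only source. The listings' columns are not shown, so this mitigates the problem without fully answering it.
- Protocol 7.2 asks for AE start and stop dates, not times. The SAP implies that a time field exists but expects some times to be missing.

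What the defence does not answer is that, when the time is recorded, the SAP knowingly places the event under a dose not yet given, in a column described as the vaccination at onset.

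**Conclusion.** The point holds within a narrow scope. For adverse events that start on a dosing day before the injection, at vaccinations 2 to 6, SAP 5.10 assigns the event to the wrong dose even though the recorded time shows this. Each affected ISR moves one count to the next column of Table 12, and its onset from the last dose becomes 0 instead of about 7 days (6 to 8). The number of such events is unknown and could be zero.

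The conclusion rests on AE start times being recorded, which the SAP implies and the protocol does not require, and on Table 12 counting events. It does not extend to the primary safety results, which are unchanged. Nor is it a contradiction between passages: it is a stated convention that discards information and gives a misleading entry. It is worth correcting because the correction is cheap and Table 12 is the only summary of how ISRs develop over the six doses.

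**What to change.** Extend the first-dose exception in SAP 5.10 to vaccinations 2 to 6, keeping column assignment and onset separate:

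- **Both times recorded, and the event starts before that day's dose:** assign the event to the previous vaccination and calculate onset from that dose.
- **AE start time or administration time missing:** keep the date-based rule for the Table 12 column only. Leave the existing SAP 5.10 provision on missing start times as it governs onset. Mark such same-day events with a footnote in Table 12.

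The separation is needed because SAP 5.10 already withholds onset when the start time is missing and the administration time was entered. A blanket same-day rule for missing times would conflict with that.

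The cost is one or two sentences, one programming condition and a footnote. The small downside is that assignment then depends partly on whether times were recorded, which the footnote makes visible. Before adopting the change, confirm that the eCRF captures AE start times, since the protocol asks only for dates.

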5.11 Decimal places

When data are used in calculations it important that rounding is only conducted when the final test result is obtained (to avoid accumulation of errors).

All percentages should be presented to 1 decimal place. If a percentage value is less than 0.1% on rounding, then use '<0.1%'.

Days to be presented to 0 decimal places.

5.12 Statistical software

Medidata Rave will be used as the Electronic Data Capture (EDC) system for the trial.

SAS 9.4 will be used to generate data listings and summary tables/graphs.

5.13 Supplementary analysis – Pharmacodynamics (data collected outside of the clinical database)

Pharmacodynamic analyses will be described in supplementary lab reports [REDACTED]. There are no primary endpoint pharmacodynamic assays for this study.

5.13.1 HLA Pre-screening

DNA extracted from whole blood taken at pre-screening will be analysed by Luminex (or similar method) for HLA-A*02:01 allelic string (*HLA population*). The whole A* allele will be reported for each patient.

Results are reported per patient within 14 days of receipt of the sample. The HLA-A*02:01 status (positive or negative) is also captured in the clinical database on the enrolment eCRF.

The final report is expected no more than two months after completion [REDACTED].

No formal statistical analysis is planned. The data will be summarised in the CSR and the final report included as an appendix.

5.13.2 Secondary endpoints

5.13.2.1 Identification of peptide specific T cells (Secondary Immunogenicity Endpoint Population)

Immunological response will be measured in whole blood (PBMCs) by hTERT specific T cells as measured by ELISPOT analysis at the following time points:

- baseline,
- vaccination weeks 3, 4 and 6,
- 2 weeks post last vaccination and
- 3, 6 and 12 months post first vaccination.

Vaccine induced ELISPOT response in blood will be reported longitudinally for each patient. The total number of patients showing durable peripheral immune response, defined as a change in one validated assay at two time points after at least two vaccinations (where a change is defined as 2.5 fold change over baseline [after removal of background], assay control and >35 spots/ 10^6 cells) will be reported.

Interim reports are expected at timepoints to be agreed between the Sponsor and the laboratory. Interim reports will be provided within one month of completing the agreed patient analyses. A final report is expected no more than 10 weeks after the last sample is analysed.

The data will be reported in tables and graphs/figures. No formal statistical analysis is planned. The results will be summarised in the CSR and the final report included as an appendix.

5.13.3 Tertiary endpoints

[REDACTED]
[REDACTED]
[REDACTED]

[REDACTED]
[REDACTED]
[REDACTED]
[REDACTED]

[REDACTED]
[REDACTED]
[REDACTED]

[REDACTED]
[REDACTED]

[REDACTED]

[REDACTED]

[REDACTED]

[REDACTED]

[REDACTED]

[REDACTED]

[REDACTED]

[REDACTED]

[REDACTED]

[REDACTED]

[REDACTED]

[REDACTED]

[REDACTED]

[REDACTED]

[REDACTED]

[REDACTED]

[REDACTED]

[REDACTED]

[REDACTED]

[REDACTED]

[REDACTED]

[REDACTED]

[REDACTED]

[REDACTED]

[REDACTED]

[REDACTED]

5.14 Other statistical analysis

5.14.1 Stratification and covariate analysis

No stratification or covariate analysis is planned.

5.14.2 Multivariate analysis

No multivariate analysis is planned.

5.14.3 Subgroup analysis

Given the small number of patients to be vaccinated, no subgroup analyses are planned.

5.14.4 Interim analysis

An interim analysis will be conducted once all patients administered AST-VAC2 have withdrawn, died or completed their 2-year follow-up visit for survival. Once this condition is met, a data cut-off will be established. All patient visits occurring on or before this date will be analysed and summarised in the clinical study report including safety data to date and assessment of OS at 2 years.

Any data collected after this date will be summarised in a supplemental report produced for the final analysis to satisfy the safety reporting requirements for AST-VAC2 as an advanced therapy investigational medicinal product (ATIMP).

The relevant data will be uploaded to ClinicalTrials.gov after the CSR is approved.

5.14.5 Final analysis

The final analysis will be conducted after one of the following conditions is met:

- The trial is terminated early (e.g. due to toxicity)
- The End of Trial has been reached (defined as the date when all patients have either withdrawn from the trial or died, or the last patient has completed their final follow-up visit [whichever is the latter]. The final follow-up visit is scheduled to take place 5 years after the patient's first vaccination).

Once one of the conditions is met, a data cut-off date will be established. All patient follow-up visits occurring on or before this date will be analysed and summarised in a supplemental report.

6. TABLE LISTINGS AND FIGURES

6.1 LISTINGS

CSR Appendix Subsection	CSR Listing Number	Listing	New Listing Name for CSR
16.2.1 Discontinued Patients	16.2.1.1	Vaccine Received	Vaccine Received
	16.2.1.2	End of Vaccination	Vaccination Completion
16.2.2 Protocol Deviations	16.2.2.1	To be provided from the central deviation tracker	N/A
16.2.3 Patients excluded from Efficacy Analysis	16.2.3.1	Enrolment	Enrolled Patients
16.2.4 Demographic and Baseline Data	16.2.4.1	Demographics	Patient Demography
	16.2.4.2	Diagnosis	Diagnosis of Primary Disease
	16.2.4.3	Medical History	Medical History
	16.2.4.4	Medical Procedures	Medical Procedures
	16.2.4.5	Prior and Concomitant Medications	Prior and Concomitant Medications
	16.2.4.6.1	Surgery	Previous Treatment for Malignant Disease - Surgery
	16.2.4.6.2	Chemotherapy/other therapy	Previous Treatment for Malignant Disease – Chemotherapy/Other Therapy
	16.2.4.6.3	Radiotherapy	Previous Treatment for Malignant Disease - Radiotherapy
	16.2.4.7	Physical Examination	Physical Examination
	16.2.4.8	Chest X-ray Results	Chest X-ray
16.2.5 Compliance and Drug Administration	16.2.5.1	Drug Administration - Vaccination	Drug Administration - Vaccination
16.2.6 Efficacy Response	16.2.6.1	Immune Response Index Lesions	Immune Response Index Lesions
	16.2.6.2	Immune Response Non-Index Lesions	Immune Response Non-Index Lesions
	16.2.6.3	Immune Related Response Criteria	Immune Related Response
	16.2.6.4	New Anti-Cancer Therapy	New Anti-Cancer Therapy
	16.2.6.5	Survival	Survival
	16.2.6.9	CEA Sample	CEA Sample
16.2.7 Safety	16.2.7.1	Adverse Events	Adverse Events

	16.2.7.2	Adverse Events by SOC	Adverse Events by SOC
	16.2.7.3	Follow-Up	Follow Up
	16.2.7.4	WHO	WHO Performance Status
	16.2.7.5	Haematology	Haematology: Haemoglobin, WBC, Neutrophils, Lymphocytes, Eosinophils, Platelets
	16.2.7.6	Biochemistry	Biochemistry: Sodium, Potassium, Adjusted calcium, Phosphate, Urea, Creatinine, Total Protein, Albumin, Bilirubin, ALP, ALT, AST, CRP
	16.2.7.7	Urinalysis	Urinalysis: Glucose, Protein, Blood, pH
	16.2.7.8	Vital Signs	Vital Signs
	16.2.7.9	Pregnancy	Pregnancy
	16.2.7.10	ECG	ECG

6.2 SUMMARY TABLES

Table Number in RAP	CSR Table Number	Table Name
Table 1	N/A	Trial Design
N/A: to be produced as part of lab reporting	In-text table	Human Leucocyte Antigen Status at Screening
Table 2	14.1.1	Summary of Patient Demography (Full Analysis Population)
Table 3	14.1.2	Primary Diagnosis at Baseline (Full Analysis Population)
Table 6	14.1.3	Summary of Baseline Disease Sites (Full Analysis Population)
Table 4	14.1.4	Summary of Prior Treatment for Malignant Disease (Full Analysis Population)
Table 5	In-text table (will refer to listing)	Summary of Prior Lines of Chemotherapy/Other Therapy (Full Analysis Population)
Table 7	In-text table (will refer to listing)	Protocol Deviations per Criterion
Table 9	14.3.1	Overview of Treatment Emergent Adverse Events (Safety Population)
Table 8	14.3.2	Frequency of All Adverse Events (Safety Population)
N/A: based on Table 8	14.3.3	Frequency of Pre-Treatment Adverse Events (Safety Population)
N/A: based on Table 8	14.3.4	Frequency of Treatment Emergent Adverse Events (Safety Population)
N/A: based on Table 8	14.3.5	Frequency of Treatment Emergent Serious Adverse Events (Safety Population)

N/A: based on Table 8	14.3.6	Frequency of Related Treatment Emergent Adverse Events (Safety Population)
Table 10	14.3.7	Frequency of Treatment Emergent Adverse Events and Related Treatment Emergent Adverse Events by Worst CTCAE Grade within an Episode (Safety Population)
Table 11	14.3.8	Frequency of Patients with Treatment Emergent Adverse Events and Related Treatment Emergent Adverse Events by Worst CTCAE Grade within an Episode (Safety Population)
Table 12	14.3.9	Summary of Injection Site Reactions by Grade and Vaccination Number (Safety Population)
Table 13	14.2.1	Overall Response (Response Population)
Table 14	14.2.2	Summary of Survival (Safety Population)
Table 15	14.2.3	Two Year Survival (Safety Population)

7. PRESENTATION OF RESULTS IN CLINICALTRIALS.GOV INCLUDING ADDITIONAL TABLES

The following information will be used for presentation and upload of trial data on ClinicalTrials.gov. The data presented will be consistent with the final CSR but will be tabulated in a format that fits with the ClinicalTrials.gov requirements¹.

The tables programmed for ClinicalTrials.gov will **not** form part of the Clinical Study Report (CSR).

7.1 Arms and Interventions

The trial will be presented as a single group design.

Data will be presented for one arm.

Treatment arm:	Participants with advanced NSCLC, to receive AST-VAC2
Treatment Arm type:	Experimental
Arm Description:	Participants will receive up to a maximum of six vaccinations over six weeks. Each weekly AST-VAC2 vaccination will be administered as a split dose via two intradermal injections at a target dose defined as 1×10^7 viable cells. There is no dose escalation planned during the study; only one dose level will be explored.
Intervention type:	Biological/Vaccine
Intervention Name(s):	AST-VAC2
Other Intervention Name(s):	N/A
Intervention Description:	Allogeneic dendritic cell vaccine.

¹ ClinicalTrials.gov Results Data Element Definitions for Interventional and Observational Studies found [here](#)
CRUKD/17/003 RAP Version: 2.0 09Mar2023 FINAL

7.2 Participant Flow

The participant flow section of the results upload will include the following details. The programmed table output for reason not completed may be re-categorised to ClinicalTrials.gov categories and reviewed by Clinical Study Manager for approval.

Period Title	Overall Study
Arm/Group Title	Experimental: AST-VAC2
Arm/Group Description	Participants will receive up to a maximum of six vaccinations over six weeks. Each weekly AST-VAC2 vaccination will be administered as a split dose via two intradermal injections at a target dose defined as 1×10^7 viable cells. There is no dose escalation planned during the study; only one dose level will be explored.
	Number of Participants
Started (participants enrolled into main trial)	*
Completed (6 vaccinations)	
Not completed	
Reason not completed	
Adverse Event	
Death	
Lack of Efficacy	
Lost to Follow-up	
Physician Decision	
Pregnancy	
Protocol Violation	
Withdrawal by Subject	
Disease Progression	

Sponsor's decision to terminate the trial	
Started (participants entered follow-up period)	
Completed (2-year OS follow up)	
Not completed	
Reason not completed	
Lost to follow-up	
Withdrawal of consent	
Death	
Declined to attend follow-up visit	

7.3 Baseline Characteristics

The baseline characteristics section of the results upload will include the following details. The programmed table output for reason not completed may be re-categorised to ClinicalTrials.gov categories and reviewed by Clinical Study Manager for approval.

Note: CDD trials don't routinely collect data on race. Ethnicity information is collected for some trials, where ethnicity information is collected, the standard category of Race will be entered as "not collected" (or equivalent) on ClinicalTrials.gov and Ethnicity information provided as an additional baseline measure.

Arm/Group Title	Experimental: AST-VAC2
Arm/Group Description	Participants will receive up to a maximum of six vaccinations over six weeks. Each weekly AST-VAC2 vaccination will be administered as a split dose via two intradermal injections at a target dose defined as 1×10^7 viable cells. There is no dose escalation planned during the study; only one dose level will be explored.
Overall Baseline Participants	Number of Participants
Baseline Analysis Population Description	*
Age, Number Analysed	
Age, Median (Full range)	
Sex, Number Analysed	
Male, number of participants	
Female, number of participants	
Ethnicity	Not collected

